#### A3a. Financial Conflict of Interest

Does any member of study personnel (Investigator (including investigator's spouse and/or dependent children)) that are involved in the design, conduct, or reporting of the research have a Significant Financial Interest (SFI) that would reasonably appear to be affected by the research for which funding is sought and/or associated with an entity/business that would reasonably appear to be affected by the research?

No

### A5. Funding Source:

Baylor College of Medicine (Internal Funding Only)

### A6b. Research conducted outside of the United States:

Country:

Facility/Institution:

Contact/Investigator:

Phone Number:

If documentation of assurances has not been sent to the Office of Research, please explain:

# A7. Research Category:

# A8. Therapeutic Intent

Does this trial have therapeutic intent?

No

#### A9. ClinicalTrials.gov Registration

Does this protocol/trial require registration on ClinicalTrials.gov due to it: meeting the definition of an Applicable Clinical Trial, being required under the terms and conditions of an award, or being proposed to be published in ICMJE journals? No, this clinical is not a clinical trial, or does not meet the definition of an Applicable Clinical Trial, or does not need to be registered under the terms and conditions of an award, or is not a clinical trial with results intended to be reported in an journal belonging to the ICMJE. Registration is not required.

#### Section B: Exempt Request

## **B. Exempt From IRB Review**

Not Applicable

#### Section C: Background Information

Blood carotenoid concentrations are a widely accepted objective biomarker of fruit and vegetable intake (1,2), which has been used in countless national surveys and epidemiological and clinical studies for over 4 decades. Nonetheless, blood carotenoid concentration measures require specialized chromatographic analysis and venipuncture for sample collection, impeding the more widespread, field use of this measure for monitoring pediatric fruit and vegetable intake. Dermal carotenoid intensity is a promising biomarker of fruit and vegetable intake in adults and children, with most research using a non-commercial Raman spectroscopy technology. Raman spectroscopic measures of skin carotenoids, however, are confounded by the presence of hemoglobin and melanin, so a newer, commercially-available technology utilizing reflectance spectroscopy (RS; Veggie Meter, Longevity Link, Corp., UT) which corrects for these confounding signals is now available (3). Non-invasive estimation of pediatric fruit and vegetable intake is an exciting prospect and is more likely to be pursued with the availability of the new RS device. Infanthood and the period

of complementary food introduction is a particularly important time during which fruit and vegetable intake should be monitored in children. This time in life may be a critical window during which infants can experience new flavors and textures, indeed leading to greater acceptance later in childhood and into adulthood (4,5). However, infant fruit and vegetable intake is difficult to objectively assess because of parental reticence about infant blood sampling and because of imprecision inherent with rapid food intake recall tools used to query caregivers. However, use of RS-measured dermal carotenoid intensity as a non-invasive biomarker of fruit and vegetable intake must be validated on a number of parameters before it can be reliably deployed for research, clinical use, or community monitoring.

To definitively develop dermal carotenoid intensity as a biomarker of infant fruit and vegetable intake, we ultimately must conduct controlled feeding studies. In controlled studies, the dietary carotenoid inputs and dermal carotenoid responses will be carefully quantitated and can be correlated to develop predictive models relating the two, along with relevant covariates. However, before proposing controlled feeding studies in infants, we must address the following questions specific to this pediatric population: 1) Is skin carotenoid measurement feasible in infants at the finger and heel? 2) How do replicate measurements effect measurement reliability? 3) What are the mean skin carotenoid scores observed across infancy? 4) What are the mean carotenoid intakes and plasma carotenoid concentrations observed in infancy. 5) Are plasma carotenoid concentrations and carotenoid intakes associated with skin carotenoid scores in infants? Primary analyses will focus on 4 month olds.

#### Section D: Purpose and Objectives

- Aim 1: To determine the feasibility and reliability of skin carotenoid measurement in infants.
- Aim 2: To determine the mean carotenoid intakes and mean plasma carotenoid concentrations in infants.
- Aim 3: To assess the validity of skin carotenoid scores as a correlate of plasma carotenoid concentrations and carotenoid intake in infants.
- Aim 4. To determine the relative validity of different infant dietary assessment tools for estimating infant carotenoid intake, energy intake, and food group intake at 4, 6, and 8 months of age.

# Section E: Protocol Risks/Subjects

#### E1. Risk Category

Category 1: Research not involving greater than minimum risk.

## E2. Subjects

Gender:

Both

Age:

Adult (18-64 yrs), Geriatric (65+ yrs), Infant/Toddler (0-36 mos)

Ethnicity:

All Ethnicities

Primary Language:

English

Groups to be recruited will include:

Healthy, non-patient, normals

Which if any of the following vulnerable populations will be recruited as subjects?

Children, Women of child bearing potential

Vulnerable populations require special protections. How will you obtain informed consent, protect subject confidentiality, and prevent undue coercion?

The subjects in this study will be healthy, post-partum women of childbearing age along with their healthy infants. Informed, written consent will be obtained from all women participating in the study. The adult participants will be healthy subjects with decisional capacity. During the informed consent process we will inform the adult participants that there is no direct benefit to them or their infants for participating in the study. The infants are too young to provide assent, so informed consent will be obtained from their parents on their behalf.

#### E3. Pregnant woman/fetus

Will pregnant women and/or fetuses (as described in 45 CFR 46 Subpart B) be enrolled in the research? No

#### E4. Neonates

Will neonates of uncertain viability or nonviable neonates (as described in 45 CFR 46 Subpart B) be enrolled in the research?

No

#### E5. Children

Will children be enrolled in the research?

Yes

# Section F: Design/Procedure

## F1. Design

Select one category that most adequately describes your research:

z.s) Biomarker/Gene Association Study

Discuss the research design including but not limited to such issues as: probability of group assignment, potential for subject to be randomized to placebo group, use of control subjects, etc.

This is a prospective observational study of the associations between a non-invasive biomarker of fruit and vegetable intake, dermal reflectance, with reported dietary fruit and vegetable intakes and blood biomarkers of fruit and vegetable intake (blood carotenoid concentrations). There are no placebo or control groups.

#### Inclusion Criteria:

Inclusion: infant is 4-4.5 months old at baseline; was born at term (>/=37 weeks gestation); is within the 5th-95th weight-for-age percentile (inclusive); primary caregiver can speak, read, and understand English; infants are exclusively breast- and/or formula-feeding at baseline. Exceptions to exclusive breast and formula feeding can be made if the infant has been fed a single-grain infant cereal, as is customary in some ethnic populations in Houston, or has consumed equal to or less than 1 teaspoon of solid food per week. Consenting parent or caregiver must be 18 years old or older.

#### **Exclusion Criteria:**

Exclusion: If infant has a sibling enrolled in the trial they are not eligible to participate. Infants will be excluded if the infant has a metabolic, digestive, or malabsorptive disorders; has a known bleeding or clotting disorder; requires a special diet; is exposed to tobacco smoke in the home; is currently taking any isolated carotenoid supplements; is using medications or complementary or alternative medications that interfere with dietary fat absorption; and/or has a history of endocrine disorders requiring hormone administration.

#### F2. Procedure

Overall Study Design: Caregivers will be phone pre-screened to review subject eligibility. Pre-screened subjects and the primary caregiver will be invited to the Children's Nutrition Research Center (CNRC) Metabolic Research Unit (MRU) for on-site screening, consent, and baseline 4-month-old assessments between 4 and 4.5 months of age. Subjects and their primary caregiver will return between 6-6.5 and again between 8-8.5 months of age. At each visit,

caregivers will complete a 7 day food frequency questionnaire (FFQ) on behalf of the infant, an optional infant blood sample will be drawn, infant dermal carotenoid intensity, length, weight, and body fatness will be measured. One week prior to the 6- and 8-month-old visits, the primary caregiver will complete an online secure food intake questionnaire for 3 separate days to provide a 24-hour dietary recall for the infant. A research staff member may contact the caregiver the next day about any questions regarding the 24 hour dietary recall. Lactating mothers will be asked to provide an optional breast milk sample at study visits if they are currently breastfeeding.

Contact 1: Recruitment (less than 1 hour): Subjects will be recruited in-person, by posted flyers, or be social media advertising. For details on recruitment locations, see the attachment "H-43692 Recruitment Sites".

Contact 2: Pre-screening phone/secure video call or in-person interview (less than 1 hour): Review of eligibility and invitation for consent and enrollment will be accomplished by e-mail, phone call, or with the participant's permission, in-person at the point of recruitment. The interested adult will be pre-screened to assess general availability and eligibility for the study. If deemed potentially eligible, they will be invited to the CNRC or secure video call for Contact 3a. If too young, we will waitlist and phone/text/email to confirm eligibility/interest.

Contact 3a: Screening, consent, and enrollment (virtual or in-person) (2 hours): Eligible volunteers will be invited to the CNRC MRU or secure video call for advanced screening of inclusion/exclusion criteria. Eligibility will be reviewed with the research staff by a questionnaire and anthropometric measures taken by nursing or research staff or parent-reported infant weight if by video-call. Parent-reported infant weight will be confirmed during in-person visit 1. Those meeting the inclusion criteria will be invited to consent and enroll. The informed consent will be reviewed by video call, and subjects will be asked to sign an electronic PDF and/or paper copy of the consent forms and return the signed electronic consent or picture of the signed paper consent by e-mail. Alternatively, secure electronic consent forms on RedCap may be used which both parties. Upon receipt, the staff will move forward with virtual education and orientation, query infant demographics (race/ethnicity and sex), and parent contact information. In order to provide financial compensation via the ClinCard (debit card) we are required to collect their social security number. We will not use this number for subject tracking or elsewhere in our records.

Contact 3b: Visit 1 (1 hour): If consent was conducted virtually, wet-signed consent forms will be received upon arrival to the CNRC for in-person visit 1. At the CNRC, infant length, weight, and skinfold thickness will be measured. Those that consent and enroll will complete a food frequency questionnaire for their infant, will provide an optional 10 mL breastmilk sample (if they are currently lactating) for baseline carotenoid and vitamin A status analysis, and an optional blood sample will be provided by the infant (4-8 mL) for baseline blood carotenoid and vitamin A status. Infant dermal carotenoids will be measured at the finger and heel.

Anthropometry: Infant height and weight will be measured visits using standard procedures (measured 3x). Infant fat mass will be estimated from skinfold thickness by validated equation (1) at the 4, 6, and 8 month visits. Trained staff will collect the data.

Dietary Assessment: At each study visit, usual infant consumption of breast milk and/or formula intake (including brand), fruits and vegetables, and other carotenoid-rich foods (e.g. eggs) will be assessed by 7 day recall using a validated infant food frequency questionnaire (FFQ) (2). This FFQ is analyzed using Nutrient Data System for Research (Univ Minnesota) software by the MRU registered dietician ([name], RD) and yields food group and nutrient intake data including carotenoids. Dietary intake will be assessed during the 1 week prior to the 6- and 8-month-old study visits through 3x24 hour dietary recalls (2 weekdays and 1 weekend day) using ASA24 (NIH/NCI), a confidential, online tool. In order to assist caregivers in remembering and finding out about what their infant ate each day, they will be given an Infant Food Diary in which to record everything their infant ate during the queried 7 day period. The Food Diaries will be collected at visits 2 & 3 for our records. Research staff will follow-up with the subjects by phone to clarify any food responses as needed. These 24 hour recalls will be analyzed for energy intake, fruit and vegetable servings, and carotenoid intake. If the participants cannot access the ASA24 food survey using their device, the research staff will call them by phone and ask the ASA24 questions in order to complete the recall.

Dermal Carotenoid Assessment: Pressure-mediated RS ("Veggie Meter") will measure dermal carotenoid intensity. Before use, the device is calibrated. The same index finger of the infant is cleaned with an alcohol wipe and placed on the device's lens for 10 s at each visit. Triplicate readings are recorded electronically. Because some infants' fingers may be too small to obtain a reproducible reading, we will also collect a back-up measurement of the infant's heel using the same procedure as for the finger. This device will not diagnose or treat a disease or condition, so will not require FDA Investigational Device Exemption.

Plasma and Breast Milk Sample Collection: All samples will be collected and handled in low light to prevent carotenoid degradation. Infants' blood (4-8 mL, no more than 3 mL/kg body mass) will be collected by venipuncture into evacuated tubes by nursing staff. If venipuncture is unsuccessful, a heel (at 4 months) or toe prick (at 6 or 8 months) by lancet can be used for capillary sampling (up to 2 mL). Plasma will be aliquoted immediately after collection and stored at -80 °C for carotenoid analysis and inflammatory cytokine analysis. Lactating mothers have the option to pump total breast milk from one breast (the first breast from which the infant fed at the prior feeding, >1 h prior) manually (Harmony Breast Pump, Medela, IL), total volume recorded, and a 10 mL sample will be collected, lipid content analyzed by the creamatocrit method (3), and the remainder stored at -80 °C for carotenoid analysis and inflammatory cytokine analysis. Milk lipids are measured for descriptive purposes as milk carotenoids correlate with milk lipids (4). Remaining

expressed milk can be offered to the infant.

Contact 4, 5, 6, 7: 3 x 24 hour recalls of infant dietary intakes (45 min each): During the 1 week period after the 4-4.5 month old visit, the research coordinator will call/text/email the primary caregiver to notify them that they should begin recording their infant's food and drink in the food diary, and complete an online 24 hour dietary intake recall using ASA24 for the infant from two weekdays and one weekend day. If needed, research staff will place a follow-up call to clarify any information needed from the online dietary recall. Contact 8: Reminder of upcoming visit and 24 hour recall phone calls (5 min): The primary caregiver will be contacted by phone/text/email to confirm subject availability and instructions for preparing for their 24 hour dietary recalls. They will be asked to provide contact information for any additional caregivers that should be interviewed about the dietary intake of the child.

Contacts 9, 10, 11, 12: 3 x 24 hour recalls of infant dietary intakes (45 min each): During the 1 week period before the 6-6.5 month old visit, the research coordinator will instruct the caregiver as described for Contacts 4-7.

Contact 13: Reminder of upcoming visit (5 min): The primary caregiver will be reminded of the date and time of the 6 month study visit.

Contact 14: 6-month study visit (2 hours): The primary caregiver and infant will come to the CNRC MRU between the ages of 6-6.5 months old. Caregivers will complete a semi-quantitative FFQ reflecting on the dietary intakes of their infant during the past 7 days. Infant dermal carotenoids will be measured by pressure-mediated reflectance spectroscopy, infants will provide an optional blood sample (4-8 mL) for carotenoid and vitamin A analysis, and lactating mothers will be asked to provide an optional breast milk sample (10 mL). Infant length, weight, and skinfold thickness will be measured.

Contacts 15, 16, 17, 18: 3 x 24 hour recalls of infant dietary intakes (45 min each): During the 1 week period before the 8-8.5 month old visit, the research coordinator will instruct the caregiver as described for Contacts 4-7.

Contact 19: Reminder of upcoming visit (5 min): The primary caregiver will be reminded of the date and time of the 8 month study visit.

Contact 20: 8-month study visit (2 hours): The primary caregiver and infant will come to the CNRC MRU between the ages of 8-8.5 months old. Caregivers will complete a semi-quantitative FFQ reflecting on the dietary intakes of their infant during the past 7 days. Infant dermal carotenoids will be measured by pressure-mediated reflectance spectroscopy, infants will provide an optional blood sample (4-8 mL) for carotenoid and vitamin A analysis, and lactating mothers will be asked to provide an optional breast milk sample (10 mL). Infant length, weight, and skinfold thickness will be measured.

## Section G: Sample Size/Data Analysis

### G1. Sample Size

How many subjects (or specimens, or charts) will be used in this study?

Local: 21 Worldwide: 21

Please indicate why you chose the sample size proposed:

A final n=21 is sufficient to estimate the mean time required to measure skin carotenoid concentrations in 4 month olds, to estimate the reliability of skin carotenoid score measurements in 4 month olds, obtain estimates for mean and SD skin carotenoid scores in 4 month olds, and examine the correlation between skin carotenoid scores and plasma carotenoid concentrations and carotenoid intake in 4 month olds.

## G2. Data Analysis

Provide a description of your plan for data analysis. State the types of comparisons you plan (e.g. comparison of means, comparison of proportions, regressions, analysis of variance). Which is the PRIMARY comparison/analysis? How will the analyses proposed relate to the primary purposes of your study?

Experimental Question 1: Assess the feasibility of triplicate skin carotenoid measurements in infants by calculating the mean time required for measurement.

Approach - mean time to measure skin carotenoid scores in triplicate at the finger and heel were calculated in 4, 6, and 8 month olds (primary endpoint is 4 month old measurements).

Experimental Question 2: The effect of replicate measurements (3 versus up to 6 replicates) on measurement reliability in 4, 6, and 8 month olds.

Approach: Calculate the intraclass correlation coefficients and 95% confidence intervals using generalized linear mixed models with restricted maximum likelihood. Models specify a random replicate effect with nesting of replicates within infant and no covariates. ICC is calculated by dividing the variance effect for replicate by the total variance.

Experimental Question 3: Calculate the mean skin carotenoid scores, plasma carotenoid concentrations, and carotenoid intakes in infants.

Approach: Mean and standard deviation skin carotenoid scores, plasma carotenoid concentrations, and carotenoid intakes are calculated for 4, 6, and 8 month old infants.

Exploratory Questions: The correlation between skin carotenoid scores, at the finger or heel, with dietary carotenoid intake and total plasma carotenoid concentrations in 4, 6, and 8 month olds.

Approach: Generalized linear mixed models controlled for age, skin measurement location, and their interaction, with either plasma carotenoids or dietary carotenoid intake as predictors of the outcome skin carotenoid scores.

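### Minor, cheap improvement: feasibility is judged only by mean triplicate time, which cannot show in how many infants a usable triplicate was obtained at the finger or the heel

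*Combined protocol and SAP*

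**What the plan says.** Aim 1 in Section D is "To determine the feasibility and reliability of skin carotenoid measurement in infants". Among the questions that Section C wants answered before controlled feeding studies is "Is skin carotenoid measurement feasible in infants at the finger and heel".

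G2 turns feasibility into one statistic. Experimental Question 1 is "Assess the feasibility of triplicate skin carotenoid measurements in infants by calculating the mean time required for measurement", and its approach is that "mean time to measure skin carotenoid scores in triplicate at the finger and heel were calculated in 4, 6, and 8 month olds", with the 4-month measurements as primary. G1 supports the sample size for this question in the same terms: "A final n=21 is sufficient to estimate the mean time required to measure skin carotenoid concentrations in 4 month olds".

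On the measurement itself, F2 says under Visit 1 that "Infant dermal carotenoids will be measured at the finger and heel". Under Dermal Carotenoid Assessment it says that "Because some infants' fingers may be too small to obtain a reproducible reading, we will also collect a back-up measurement of the infant's heel". The same paragraph has the three readings stored electronically.

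Reliability is a separate item, Experimental Question 2: "The effect of replicate measurements (3 versus up to 6 replicates) on measurement reliability in 4, 6, and 8 month olds". It is analysed by intraclass correlation.

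**The concern.** The background question is whether the measurement can be made in infants at these two sites. The planned statistic describes how long it takes. A mean triplicate time could be short and stable while an unknown share of infants gave no usable finger triplicate, and nothing in the planned output would report that share.

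The protocol itself foresees a problem at the finger and adds the heel for that reason. The plan has no statistic showing how often the problem arose, or whether the heel worked where the finger did not. A report that followed the plan exactly could therefore state a feasibility result for Aim 1 without saying in how many infants each site worked.

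**Working it through.** **1. Is the count planned anywhere?**

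- Section C: feasibility at finger and heel is asked as a question.
- Section D, Aim 1: feasibility is named beside reliability.
- F2: both sites are measured, the heel as a back-up because of possible poor reproducibility at the finger. No definition of a usable or failed reading is given.
- G1: only mean time is named for feasibility.
- G2, Question 1: only mean time, by site and age. There is no count or proportion, no threshold, and no rule for an infant without a usable triplicate.
- G2, Question 2: the intraclass correlation bears partly on reproducibility. It is not stated by site, and as a ratio of variances it gives no number of infants.

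No section supplies the count.

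**2. The plan's own figure.** G1 states n = 21. It cannot be reproduced, because no standard deviation of time, precision target, power or alpha is given. The point does not depend on it. For reference, the 95% half-width for a mean from 21 infants is t(0.975, 20)/√21 = 0.455 SD. This is the precision of a duration and says nothing about how many infants succeeded.

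**3. What the added proportion would show.** For x infants with a usable triplicate out of n = 21, the exact (Clopper-Pearson) two-sided 95% limits are:

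- lower = Beta quantile at 0.025 with parameters x and n − x + 1
- upper = Beta quantile at 0.975 with parameters x + 1 and n − x (upper = 1 when x = n)

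| x/21 | Proportion | 95% CI |
|---|---|---|
| 21 | 100% | 83.9% to 100% |
| 20 | 95.2% | 76.2% to 99.9% |
| 18 | 85.7% | 63.7% to 97.0% |
| 15 | 71.4% | 47.8% to 88.7% |

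For 21/21 the lower limit reduces to 0.025^(1/21) = 0.839. The counts are illustrations, since the documents give no expected completion rate.

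**4. Would 21 infants reveal failures at all?** With a true failure probability p per infant, the chance of at least one failure is 1 − (1 − p)^21. Over an assumed range of p:

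- p = 0.05: 1 − 0.95^21 = 0.659
- p = 0.10: 1 − 0.90^21 = 0.891
- p = 0.20: 1 − 0.80^21 = 0.991

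A failure rate of 10% or more at a site would therefore probably appear in the count, although its size would be poorly estimated.

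**The case against.** The strongest reply is that the plan says what it means by feasibility, namely the time burden of triplicate measurement. A 21-infant observational study without a feasibility threshold is entitled to that choice. Nothing is miscalculated or contradictory. This stands, and it keeps the point minor. It does not make mean time an answer to the question in Section C.

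A second reply is that the n beside each mean would reveal failures. At 4 months this has force. The measurement belongs to the baseline visit, so a missed visit is a weak explanation for a low n, though not an impossible one, because consent may be given by video call first. However, the plan does not promise that n, and a triplicate with poor readings can still be timed and counted.

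A third reply concerns cost. F2 says that readings are stored; it does not say that failed or abandoned attempts are. This also stands, and the fix allows for it.

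Three stronger readings are tempting, and the documents do not support them:

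- A reader might infer that mean time is biased because only successful infants contribute. The plan states no such exclusion, and the documents give no times or failure rates from which to size a bias.
- A reader might take the allowance of up to six replicates to make the word triplicate ambiguous. That allowance belongs to Question 2, on reliability; Question 1 and F2 both speak of triplicates.
- A reader might infer from Section I that later feeding studies need this count in order to choose a site. Section I says only that the preliminary data will support proposing such studies. It does not mention choosing between finger and heel.

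**Conclusion.** The point holds as a minor, inexpensive improvement. Mean triplicate time is the only planned feasibility measure, and it cannot show in how many infants a usable triplicate was obtained at either site. A count by site and age would let the study answer its own feasibility question more directly.

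The size of any harm cannot be stated, because the documents give no completion rate. The intervals above show only how precise the added statistic would be. They assume that all 21 infants are attempted at the site and age in question, and they widen if fewer are. The proportion should be read as descriptive.

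**What to change.** In G2, Experimental Question 1:

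1. Keep mean time, and report its n by site and age.
2. Add a descriptive feasibility measure for the finger and for the heel at 4 months (primary), 6 months and 8 months: number of infants attempted, number with three usable readings, and the proportion with an exact 95% confidence interval.
3. Show a finger-by-heel cross-table of success at each age, without a test.
4. Define a usable reading, and state whether the definition was set before or after data collection. The approach already speaks of times in the past tense, so data may exist.
5. Log failed attempts from now on if this is not already done. If past failures were not logged, use infants who attended the visit as the denominator, and say that this mixes failed with not attempted.

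The cost is plan wording, a tabulation of stored readings and, where needed, a short log of attempts. No extra infants, visits or procedures are required. The drawbacks are an imprecise proportion at this sample size and, if the definition comes late, the need to disclose that.

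### Feasibility is judged only by mean time to a triplicate, which has no value for an infant without three usable readings, and no completion proportion is planned

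*Combined protocol and SAP*

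**What the plan says.** Section D makes feasibility part of Aim 1: "To determine the feasibility and reliability of skin carotenoid measurement in infants". Section C lists it first among the questions to settle before controlled feeding studies are proposed: "Is skin carotenoid measurement feasible in infants at the finger and heel".

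G2, Experimental Question 1, turns this into a single quantity: "Assess the feasibility of triplicate skin carotenoid measurements in infants by calculating the mean time required for measurement". The approach is a mean by site and age, "mean time to measure skin carotenoid scores in triplicate at the finger and heel were calculated in 4, 6, and 8 month olds", and the parenthesis that follows fixes the time point: "primary endpoint is 4 month old measurements".

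F2, under Dermal Carotenoid Assessment, foresees difficulty at one site: "Because some infants' fingers may be too small to obtain a reproducible reading". Its response is a second site: "we will also collect a back-up measurement of the infant's heel using the same procedure as for the finger".

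The documents do not define a failed or abandoned attempt, a maximum number of attempts, a time limit, or when the clock starts and stops. They give no value for an infant without three usable readings and plan no proportion successfully measured. G1 sets n=21 without an allowance for failures.

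**The concern.** A time to completion exists only for infants who complete. An infant in whom three usable finger readings are never obtained contributes no finger time. The heel back-up supplies a heel time for that infant but does not fill the missing finger time.

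A plain mean needs one number per infant, and G2 supplies none for this case. If such infants occur, the mean therefore describes the infants with a completed triplicate at that site. Failure to obtain a triplicate is the most direct evidence against feasibility, yet it would appear nowhere in the only planned feasibility measure. A finger mean from 17 of 21 infants could look the same as one from 21 of 21. The stake is the question in Section C that is meant to be answered before feeding studies are proposed.

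**Working it through.** **Inputs from the documents.** n=21 (G1); three readings per site for the time endpoint (F2, G2); 4 months primary (G2). No SD of times, target precision, failure rate or time limit is given.

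**1. The plan's own figure.** G1 calls 21 sufficient to estimate the mean time, but gives nothing from which 21 can be reproduced. What it delivers is a 95% CI half-width of t(0.975, 20)/√21 = 2.086/4.583 = 0.455 SD. With 17 completers it is 2.120/4.123 = 0.514 SD.

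**2. Could the gap matter at n=21?** For an assumed failure rate p, the chance of at least one failure is 1 − (1 − p)^21:

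| p (assumed) | Chance of at least one failure |
|---|---|
| 2% | 34.6% |
| 5% | 65.9% |
| 10% | 89.1% |
| 20% | 99.1% |

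**3. How the all-infant mean depends on the value given to failures.** Let m be the completer mean, f the number of failures, and k·m the time charged to each failure. Then the all-infant mean is [(21 − f)m + f·k·m]/21 = m[1 + (f/21)(k − 1)]. Excess over m:

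| f | k = 2 (assumed) | k = 3 (assumed) |
|---|---|---|
| 0 | 0 | 0 |
| 1 | 4.8% | 9.5% |
| 2 | 9.5% | 19.0% |
| 4 | 19.0% | 38.1% |

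The excess is positive when k > 1 and negative when k < 1.

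**4. Why the time of abandonment is a poor value.** Assume 15 s per attempt, a limit of 8 attempts (120 s), and infant-specific success probabilities from Beta(4,2), Beta(3,2) and Beta(2,2).

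- If every failed infant is taken to the limit, the completer mean is shorter than the mean over all infants: 64 v 69 s for Beta(4,2) and 72 v 85 s for Beta(2,2).
- If staff stop after two consecutive failed attempts, the all-infant mean using stop times falls below the completer mean: 51 v 54, 51 v 55 and 49 v 56 s.
- If staff stop after three, the two nearly agree: 61 v 60, 63 v 62 and 64 v 65 s.

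A hand example shows the mechanism. Take 19 completers averaging 54 s and 2 failures abandoned after two attempts (2 × 15 = 30 s). Scored at the stop time, the mean is (19 × 54 + 2 × 30)/21 = 1086/21 = 51.7 s, so the failures make the site look quicker. Scored at 120 s, it is (1026 + 240)/21 = 1266/21 = 60.3 s. If the maximum is no shorter than any completed time, k is at least 1 and a failure cannot shorten the mean.

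**5. What a completion proportion would say.** Exact (Clopper-Pearson) 95% CIs:

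| Completed | Proportion | 95% CI |
|---|---|---|
| 21/21 | 100% | 83.9 to 100 |
| 20/21 | 95.2% | 76.2 to 99.9 |
| 19/21 | 90.5% | 69.6 to 98.8 |
| 17/21 | 81.0% | 58.1 to 94.6 |

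**The case against.** The strongest reply has four parts.

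- **A reading that is not reproducible is still a reading.** Three discordant values make a triplicate with a time, and the discordance belongs to the reliability analysis in Experimental Question 2. This stands in part: F2 does not say that a triplicate may be unobtainable, and its wording is conditional. But neither F2 nor G2 says what counts as a usable reading, so whether such an infant has a time is left open.
- **The plan is silent on failures; it does not say they are dropped.** This stands. The completers-only mean results from having no rule and is not a stated choice.
- **Direction and size are not fixed by the documents.** This also stands. A reader might infer that the primary mean is too short by some 7% to 16%. Those figures assume both the failure rates and that every failed attempt runs to a limit of eight. With early stopping, the comparison against stop times reverses.
- **No planned decision is shown to change.** There is no feasibility threshold. A reader might infer that finger-heel or 4-to-8-month comparisons of time are distorted, but G2 plans no such comparison: it reports mean times by site and age. Age and location enter a model only in the exploratory analysis, where the outcome is the skin score.

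None of this supplies a completion proportion or a value for an uncompleted triplicate.

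**Conclusion.** The point holds as a gap in the definition of the primary endpoint. Feasibility rests on one mean, which cannot register an infant without three usable readings at a site, and nothing beside it does so. F2 foresees that some fingers may be unsuitable, so this is more than a missing detail.

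The conclusion is conditional. With no failures, the mean is complete and the effect is zero. With failures, it describes infants with a completed triplicate only, by an amount that the documents do not allow one to compute. The figures above rest on assumed failure rates and times.

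It would go too far to say that the mean comes from cooperative infants. The documents do not mention cooperation; the one cause they name is finger size. Nor do they support a stated percentage of bias.

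**What to change.** In G2, Experimental Question 1, analyse every infant in whom a measurement is attempted, separately for finger and heel, with 4 months primary:

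1. Report the proportion with a completed triplicate, with an exact 95% CI. State what counts as a usable reading and when the clock starts and stops.
2. Report the mean and median time restricted to a fixed maximum set by the team. Score every uncompleted triplicate at that maximum and not at the time the attempt was abandoned, because early abandonment would make a failing site look quick.
3. Keep the completers-only mean as a secondary figure.

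The cost is a few sentences in G2; no extra infants, staff or procedures are needed. The restricted mean depends on the maximum chosen and will be somewhat longer than the completers-only mean if there are failures. G2 describes the times in the past tense, so measurements may already have been made. The fix still works if stop times of failed attempts were not recorded, because it needs only the fact of non-completion and the times of completed triplicates.
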